2.1 Primary Objective

Relative Vaccine Effectiveness

To demonstrate the superior relative effectiveness of QIV-HD as compared to QIV-SD among persons 65 years of age and older for the prevention of cardiovascular and/or respiratory hospitalizations

The endpoints for the primary objective are presented in Section 9.1 of the protocol.

2.2 Secondary Objectives

Relative Vaccine Effectiveness

- 1) To assess the clinical relative effectiveness of QIV-HD as compared to QIV-SD in prevention of:
 - inpatient hospitalization (using primary discharge diagnosis) for selected International Classification of Diseases, Tenth Revision (ICD-10) codes separately
 - death, either all-cause or cardiovascular or respiratory causes
 - inpatient hospitalization (using primary and secondary discharge diagnoses)
 - inpatient hospitalization (using admission diagnoses)
 - hospital emergency room visits
 - primary care visits to physician
- 2) To assess the clinical relative effectiveness of QIV-HD as compared to QIV-SD in prevention of MACE
- 3) To assess the characteristics of inpatient hospitalization or hospital emergency room visits or primary care visits to physician due to cardiovascular or respiratory event by QIV-HD and QIV-SD groups
- 4) To describe the clinical relative effectiveness of QIV-HD as compared to QIV-SD by age group and by group with specific comorbidities
- 5) To describe the clinical relative effectiveness of QIV-HD as compared to QIV-SD for different periods of observation

Safety

To describe all serious adverse events (SAEs) (including adverse events of special interest [AESIs]) for all subjects in both QIV-HD and QIV-SD groups

The endpoints for the secondary objectives are presented in Section 9.2 of the protocol.

2.3 Observational Objectives

To evaluate the QIV-HD as compared to QIV-SD in terms of:

- 1) Clinical relative effectiveness over an extended period of time
- 2) Follow-up of functionality / dependence during the 3 periods of follow-up (ie, between ≥ 14 days after vaccination and up to 31 May and 31 August of each year and during the influenza peak period)
- 3) Health Care Utilization during the 3 periods of follow-up described above
- 4) Laboratory-confirmed influenza and invasive bacterial diseases as captured in the database based on routine practice between ≥ 14 days after vaccination and up to 31 May of the year following the vaccination and during the influenza epidemic period as defined by the Finnish epidemic thresholds

The endpoints for the observational objectives are presented in Section 9.3 of the protocol.

3 Description of the Overall Trial Design and Plan

3.1 Study Design

QHD00012 was a Phase IIIb/IV, randomized, modified double-blind, active-controlled, single center pragmatic study to assess the relative vaccine effectiveness of the QIV-HD as compared to QIV-SD in approximately 121 000 adult subjects 65 years of age and older were to be enrolled over multiple influenza seasons beginning in 2019-2020 in Finland.

This study was conducted in Finland by THL, a research institute under the Finnish Ministry of Social Affairs and Health which undertakes research projects using national registers carried out in close collaboration with either Finnish or international partner. THL, as the Principal Investigator, collaborated with multiple Health Stations (HSs) overseen by selected Health Care Centers (HCC) to carry out the study and was responsible for the coordination of the operational aspects of the study conduct. THL also provided medical and study related expertise.

The study was designed to follow the routine vaccination medical practices used at the HS during the influenza vaccination campaign. The Sub-Investigators at the HCC (ie, HCC physicians) and the HS nurses were trained on the study procedures and considered qualified on the study. The Sub-Investigators guaranteed medical oversight of the vaccination visits and to respond, where needed, to any medical questions (primarily through telephone consultations). The HS nurses were responsible for routine health follow-up and immunizations.

The subject's active participation in the study was limited to the enrollment and vaccination visit.

The follow-up period in this study was defined as the data collection period. The data collection period varied based on the study objectives with the data collection period extending up to 31 August of the year following the vaccination (approximately 11 months).

However, due to the impact of the COVID-19 global pandemic which created significant challenges to conducting this clinical study (see [section 1](#). Introduction for further details), the QHD00012 study was conducted from November 2019 (first subject included) to August 2020 (cut-off subject data date) only. A total of 33 096 subjects signed an ICF and 33 093 subjects were vaccinated in one of the two study groups.

3.2 Study Plan

Randomization and Vaccination

All eligible subjects were randomized to receive a single IM injection of either QIV-HD or QIV-SD at Day 0. A scratchable list was used to randomly assign subjects to either the QIV-HD group or the QIV-SD group. All subjects were observed for 20 minutes after vaccination to ensure their safety.

Recording of Data

Finland uses multiple registers to collect different health and population data. Subject data were recorded in the local medical patient file by health care professionals (HCPs). From patient files the data was transferred automatically to the corresponding Finnish health registers (hospital diagnosis/treatment and SAEs).

Collection of Datasets

The datasets were collected using multiple Finnish health registers and compiled by THL into an analysis database. The subject's Personal Identity Code (PIC) constituted the common key between all of the registers. On a regular basis, THL extracted the study data from the different Finnish registers and when required from local medical patient files. THL submitted protocol-defined datasets to Sanofi Pasteur in a pseudonymised manner (ie, PIC will not be transferred to Sanofi Pasteur to maintain data privacy).

Collection of safety data

Serious adverse reactions (SARs) and AESIs, experienced by the subject and suspected to be related to the vaccine according to the HCP assessment, were collected using an SAR/AESI paper form throughout the study (ie, from inclusion up to 31 August of the year following the vaccination). All fatal SAEs, irrespective of causality, were collected for the same period using real-time surveillance of population data. Additional data could be collected from the local medical patient file, as needed.

All SAEs resulting in hospitalization were collected by THL from the Finnish health registers up to 6 months after vaccination. AESIs, which had not been reported by the HCPs, were collected from the Finnish health registers up to 6 months after vaccination, and reported as eSAE.

Note: AESIs included new onset of Guillain-Barré syndrome (GBS), encephalitis / myelitis (including transverse myelitis), Bell's palsy, optic neuritis, and brachial neuritis.

4 Endpoints and Assessment Methods

See Section 9 of the protocol.

With the decision of stopping the study after the first year, the endpoints correspond only for the season 2019-2020. In addition, no influenza epidemic period was defined for 2019-2020 season, as only low/moderate flu incidence was observed in Finland.

Focus on input data:

A Data Transfer Agreement (DTA) document is available as version 4.0, and describes all data available for the study. The 12 panels available are the following:

- Thl_enr, linked to enrollment and injection
- Thl_drop, that identified subject withdrawal
- Thl_dev, that identified deviations at subject level
- Thl_hilm, corresponding to hospitalizations from HILMO registry
- Thl_er, corresponding to emergency room visits from HILMO registry
- Thl_avoh, corresponding to primary care visits to the physician from AVOHILMO registry
- Thl_hvac, corresponding to previous vaccinations (flu and pneumonia) from AVOHILMO registry
- Thl_lab, corresponding to positive flu and invasive bacterial detection from NIDR registry
- Thl_chro, corresponding to aggregated data for chronic diseases (comorbidity) from Social Insurance Institution (KELA) reimbursement registry
- Thl_cara, corresponding to aggregated data for care allowance due to disability from Social Insurance Institution (KELA) reimbursement registry
- Thl_med, corresponding to aggregated data for antimicrobial medications from Social Insurance Institution (KELA) reimbursement and prescription registries
- eSAE, corresponding to SAE entered by THL in SP eCRF database (death, related SAE, and AESI), and later available in SP PV database with MedDRA coding

In addition, 3 dictionaries are available for statistical analysis:

- ICD-10 codes: It corresponds to ICD-10 codes used at Finland level. Some adaptations are also applied (eg, code such as '###*' are simplified with '###').
- ICPC-2 codes: It corresponds to ICPC-2 codes used at Finland level.
 - One file contains all codes (even not linked to selected I/J ICD-10 codes).
 - One file with only codes linked to primary objectives, and with correspondences to the ICD-10 codes.

- MedDRA: eSAE panel already contains the MedDRA codes/labels. Therefore, no external dictionary is used.

Complementary to the files above, we also have two randomization files: the randomization of the subjects based on randomization order, and the randomization of the product (dose number).

We also have a file corresponding to the 41 HS (name, link with HCC) involved in the study.

The statistics Finland registry is finally not used as source data. The eSAE is used for death information.

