Study Design, Schedule of Study Procedures, and Methodology:	QHD00012 will be a Phase IIIb/IV, randomized, modified double-blind, active-controlled, single center pragmatic study in approximately 121 000 subjects 65 years of age and older in Finland.  Vaccination On Day (D) 0, subjects will be randomized to receive a single intramuscular (IM) injection of either a high-dose quadrivalent influenza vaccine (QIV-HD) or a standard-dose quadrivalent influenza vaccine (QIV-SD). All subjects will be observed for 20 minutes after vaccination to ensure their safety.  Collection of datasets The datasets will be collected using multiple Finnish health registers and compiled by THL into an analysis database.  Collection and reporting of safety data The serious adverse reactions (SARs) and adverse events of special interest (AESIs), experienced by the subjects and suspected to be related to the vaccine according to the health care professional (HCP) assessment, will be collected and reported to THL using a SAR/AESI paper form throughout the study (ie, from inclusion up to 31 August of the year following the vaccination). All other serious adverse events (SAEs) (non-fatal SAEs except those included in the primary endpoint) will be collected by THL from the Finnish health registers up to 6 months after vaccination. AESIs and fatal SAEs, which have not been reported by the HCPs, will be collected in the same manner throughout the study.

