## Table of Study Procedures

Phase IIIb/IV Study, 1 Visit, 1 Vaccination, approximately 11 months Study Duration Each Year

Visit / Contact	V01	11 months follow-up period*
Study timelines (D)	D0	D330
Informed consent	X	
Inclusion/exclusion criteria	X	
Randomization	X	
Vaccination (date of vaccination)†	X	
Collection of suspected SARs (reported by HCPs)‡, all AESIs (reported by HCPs or collected from the Finnish health registers)‡§, and all fatal SAEs		Throughout the study
Collection of all other SAEs (except those included in the primary endpoint)**		Up to 6 months after vaccination

Abbreviations: AESI, adverse event of special interest; D, day; HCPs, health care professionals; SAE, serious adverse event; SAR, serious adverse reaction; V, visit.

\* The study duration will be approximately 11 months each year. The subject's active participation in the study will be limited to the enrollment and vaccination visit (V01).

† Subjects are to be kept under observation for 20 minutes after vaccination to ensure their safety, and any reactions during this period should be documented in the local medical patient file

‡ SARs and AESIs, experienced by the subject and suspected to be related to the vaccine according to the HCP assessment, will be submitted to THL using an SAR/AESI paper form.

§ AESIs include new onset of Guillain-Barré Syndrome, encephalitis/myelitis (including transverse myelitis), Bell's palsy, optic neuritis, and brachial neuritis.

\*\* All other SAEs (except those included in the primary endpoint) and AESIs which have not been reported by the HCPs will be collected from the Finnish health registers.

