#### **9.2.2.2 Safety Endpoints**

The following endpoints for the evaluation of safety will be described for all subjects:

- Occurrence, nature (Medical Dictionary for Regulatory Activities [MedDRA] preferred term [PT] or ICD-10 codes), time to onset, seriousness criteria, and outcome of all SARs, all AESIs, and all fatal cases throughout the study
- Occurrence and nature (MedDRA PT or ICD-10 code) of non-fatal SAEs by time to onset and seriousness criteria up to 6 months after vaccination

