## 10 Reporting of Serious Adverse Events

### 10.1 Initial Reporting by the Health Care Professionals and the Principal Investigator

Data collected in the SAE eCRF for each individual case will include outcome, precise description of medical history, results of the investigation and the causal relationship between the SAE and the product administered, as evaluated by the Principal Investigator.

The HCPs at the HCC/HS will be trained to report SARs (experienced by the subjects and suspected to be related to the vaccine according to HCP assessment), and AESIs. In Addition, other HCPs in Finland will be informed about this clinical study and will be requested to report SARs and AESIs directly to the Principal Investigator (ie, THL). For reporting purposes, all HCPs will use an SAR/AESI paper form.

All fatal SAEs will be collected on an ongoing basis from the registers using the available register data as the primary source data for reporting.

Upon receipt of any SAR/AESI paper form from a HCP or identification of an AESI or fatal SAE from the health registers, the Principal Investigator or delegate sub-Investigators must report the event which occurred during a subject's participation in the study or experiment, within 24 hours after the first awareness of any THL study personnel to the Sponsor's GPV Department, the Clinical Research Associate (CRA), and the Clinical Team Leader (CTL) using an SAE eCRF in the EDC system. Every SAE must be reported, even if the Principal Investigator considers that it is not related to the vaccine. The Principal Investigator or a delegate sub-Investigator must validate the information entered on the SAE eCRF by completing the investigator validation form.

The Principal Investigator must indicate on the SAE eCRF that the event was serious and must complete the relevant SAE section of this form. An e-mail alert will automatically be sent by the EDC system to the GPV mailbox, the CRA and the CTL with relevant SAE information details.

If the EDC system is unavailable, the Principal Investigator must notify the Sponsor, using the paper version of the SAE eCRF.

The Principal Investigator must complete the paper copies of the SAE eCRF and send them to the Sponsor by one of the following means:

- In PDF format to the following e-mail address, using a method of transmission that includes password protection: [contact]
- By express mail, to the following address  
Global PharmacoVigilance, Sanofi Pasteur SA  

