4.2.2 Safety

See Section 9.2.2 of the protocol.

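### SAP 3.2 stops the register search for AESIs at 6 months, the endpoint in SAP 4.2.2 runs to 31 August, and SAP 5.7 does not list the difference

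*SAP*

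**What the plan says.** **Endpoint.** Protocol 9.2.2.2 describes the occurrence, nature, timing, seriousness and "outcome of all SARs, all AESIs, and all fatal cases throughout the study". A 6-month limit is set there only for non-fatal SAEs. SAP 4.2.2 consists of one line: "See Section 9.2.2 of the protocol".

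**Register capture of AESIs, protocol.** The Synopsis and section 5.1.3 both explain that the study period for safety runs from inclusion to 31 August of the following year, and both say: "AESIs and fatal SAEs, which have not been reported by the HCPs, will be collected in the same manner throughout the study". In the Table of Study Procedures, the row running throughout the study includes "all AESIs (reported by HCPs or collected from the Finnish health registers". Section 10.1 requires a report on "identification of an AESI or fatal SAE from the health registers" and gives no time window. One place is less clear. The double-asterisk footnote to the same table is attached to the 6-month row for other SAEs and adds that "AESIs which have not been reported by the HCPs will be collected from the Finnish health registers".

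**Register capture of AESIs, SAP.** Section 3.2 keeps HCP paper forms and all fatal SAEs to 31 August, but states "AESIs, which had not been reported by the HCPs, were collected from the Finnish health registers up to 6 months after vaccination".

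**List of changes.** SAP 5.7 records two changes to the safety endpoint: hospitalizations are analyzed without separating fatal from non-fatal events, and seriousness comes from the eSAE panel only. The AESI window is not mentioned.

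**SAR label.** Protocol 9.2.2.1 bases a SAR on the HCP's assessment, and SAP 3.2 describes SARs and AESIs on the paper form as "experienced by the subject and suspected to be related to the vaccine according to the HCP assessment". SAP 4.3.1.5 makes an eSAE a SAR when the investigator's final assessment is related. SAP 4.3.1.4 places HCP-suspected events that the investigator judged unrelated under Other eSAE.

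**The concern.** The AESIs are a short list of neurological diagnoses that the sponsor singled out, and the endpoint asks for all of them over the whole follow-up. The register search finds those that no HCP sends in on a form. If it stops at 6 months, the AESI table rests on two capture rules: forms, deaths and registers before the cut, and forms and deaths only after it.

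Nothing in the SAP's table layout would show this. The last time-to-onset class in SAP 4.3.1.2 starts at day 121 and is open-ended, so it straddles the cut. A low count in that class could be read as an absence of late AESIs when part of it reflects the end of searching. A reader who goes to SAP 5.7 for departures from the protocol would not find it either.

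**Working it through.** **1. Inputs**

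- First and last vaccination: 04NOV2019 and 23DEC2019 (SAP 4.3.3.3)
- End of data collection: 31AUG2020 (SAP 4.3.3.3)
- Vaccinated subjects: 33,093 (SAP 3.1)
- Register AESI capture: 6 months after vaccination (SAP 3.2), read here as calendar months

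**2. The plan's own figure.** Duration = end date − start date + 1. From 04NOV2019 to 31AUG2020 this gives 301 + 1 = 302 days, which matches the maximum in SAP 4.3.3.3.

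**3. Time without register capture**

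| Vaccinated | Days to 31AUG2020 | Six months ends | Days covered | Days uncovered | Share |
|---|---|---|---|---|---|
| 04NOV2019 | 302 | 04MAY2020 | 183 | 302 − 183 = 119 | 119/302 = 39.4% |
| 23DEC2019 | 253 | 23JUN2020 | 184 | 253 − 184 = 69 | 69/253 = 27.3% |

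The SAP does not define 6 months in days. If the cut falls 180, 182 or 183 days after vaccination, the uncovered time is 121, 119 or 118 days for the first date and 72, 70 or 69 for the last. The result hardly depends on the reading.

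**4. The last onset class.** Onset is event date minus vaccination date.

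- Vaccinated 04NOV2019: the class spans days 121 to 301, which is 181 days. Days 183 to 301 lie after the cut: 119/181 = 65.7%.
- Vaccinated 23DEC2019: the class spans days 121 to 252, which is 132 days. Days 184 to 252 lie after the cut: 69/132 = 52.3%.

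More than half of the time in this class is therefore without register capture.

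**5. How many AESIs could this be?** The documents give no AESI rate, so this is illustration only. Person-time after the cut, before deaths and withdrawals, lies between two bounds:

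- 33,093 × 69/365.25 = 6,252 person-years
- 33,093 × 119/365.25 = 10,782 person-years

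Assume 10 to 100 AESIs per 100,000 person-years. Then 6,252 × 10/100,000 = 0.63 to 10,782 × 100/100,000 = 10.78 would arise in that time, both arms together. Assume further that 25% to 75% of these are neither fatal nor HCP-reported. Then 0.63 × 0.25 = 0.16 to 10.78 × 0.75 = 8.09 would go unidentified.

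**6. Could the late events be found?** Protocol 9.3 needs unscheduled hospitalizations, emergency room visits and acute primary care visits, and protocol 2.3 sets one of the follow-up periods for these to 31 August. SAP 4 lists panels for all three visit types, and SAP 4.3.3.3 uses 31AUG2020 as an end date. A late AESI may therefore already sit in these panels as a coded visit. The Data Transfer Agreement that would show whether the codes are kept is not among the documents.

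**7. SAR label.** The SAP rule takes out HCP-suspected events judged unrelated. It can also add register-found deaths or AESIs that the investigator calls related without any HCP suspicion. The documents give no counts, so neither the size nor the direction of the net change can be derived.

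**The case against.** **The protocol is not uniform.** The double-asterisk footnote can be read as putting unreported register AESIs on the 6-month row, and section 10.1 sets a reporting duty without a window. This stands as a reason to reconcile the table. It does not create a 6-month protocol window: the footnote states no period of its own, while the Synopsis, section 5.1.3 and the AESI row all say throughout the study.

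**SAP 3.2 reports conduct.** It is written in the past tense and openly states the 6 months. That is fair, and the limit is not concealed. But the endpoint in SAP 4.2.2 still points to the longer window, and SAP 5.7 covers changes in conduct as well as in analysis.

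**The gap is narrow.** Only late, non-fatal AESIs that no HCP reported are affected, and the illustrative counts span about fifty-fold on assumed inputs. This stands. The counts do not establish materiality, and the 27% to 39% are shares of time.

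**A code search is not a confirmed AESI.** The definition requires new onset, and the history listed in protocol 5.2.6 includes no neurological disease. Late hits may be follow-up visits for old diagnoses, and mixing them with reviewed cases would join two standards. This stands, so unconfirmed hits belong in a separate row.

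**The SAR rule is disclosed and has some protocol support.** Protocol 9.2.2.1 also defines a suspected SAR, which involves the Principal Investigator's or Sponsor's view; the procedures table and section 11.1 use that term; and section 10.6 relies on investigator judgment for endpoint-related SARs. This largely stands, which is why the SAR label is secondary here. The rule nevertheless matches neither protocol definition: it omits the Sponsor's view and does not require an HCP report.

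**Conclusion.** The AESI table produced under SAP 3.2 is not the endpoint to which SAP 4.2.2 refers. Register capture is missing for the last 69 to 119 days per subject, 27% to 39% of the time from vaccination to 31AUG2020. This rests on the dates in SAP 4.3.3.3 and on reading 6 months as calendar months. The number of AESIs missed is unknown and probably small. The point is worth correcting because the remedy is cheap and the table would otherwise mislead on late onset.

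Five stronger readings are not supported:

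- **That the comparison between arms is biased.** The rule is the same in both arms, safety is descriptive, and the primary test is untouched.
- **That a quarter to two fifths of AESIs are missed.** The percentages are of time, and HCP-reported and fatal AESIs are still collected to 31 August.
- **That the late events are lost.** They may be present as coded visits in the hospital, emergency room or primary care panels.
- **That the SAP takes over protocol 9.2.2 unaltered.** SAP 5.7 itself modifies other parts of that endpoint.
- **That HCP-suspected events disappear.** Those judged unrelated remain visible as Other eSAE. The SAR issue concerns labelling.

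**What to change.** **AESI window**

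1. Apply the AESI code search used up to month 6 to register visit data up to 31AUG2020, and show the 6-month count alongside.
2. Report late hits that cannot be confirmed as new onset in a separate row, marked as unconfirmed.
3. If the late data cannot be searched, state both windows on the AESI table (HCP-reported and fatal to 31AUG2020, register-found to 6 months), split the class from day 121 onward at 6 months for AESIs, and list the departure in SAP 5.7.
4. Reconcile the double-asterisk footnote in the protocol's Table of Study Procedures with its AESI row.

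**SAR label (secondary).** Label the rows as investigator-related, and as HCP-suspected but investigator-unrelated. Give the HCP-suspected total where the eSAE data identify it; the documents do not show whether the extract carries that flag. Note the difference from protocol 9.2.2.1 in SAP 5.7.

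**Cost.** Sample size, power and alpha do not change. If the transferred panels keep AESI codes after month 6, the work is one code search and one table; if not, THL must run the search. The downside is coding and confirmation effort for any late hits. The fallback and the SAP 5.7 entries need only wording and one extra class boundary. SAP 5 places SAP approval before the final database and unblinding, so a change made at that stage is free of any knowledge of results by arm.
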